 - Estimation of the incidence rate (per 100 PY exposed) of each outcome, and according to individual diagnose of each outcome, during drug exposure or if the risk is not constant over the time, during periods with a constant risk.
 - Comparison of the one-year and two-year risk of each outcome during drug exposure: rivaroxaban versus VKA, and rivaroxaban versus dabigatran, using Cox proportional hazard risk model (Cox 1972) for death and Fine and Gray model (Fine 1999) for clinical outcomes in

order to take into account death as a competing risk. Hazard ratio will be presented as point estimate with their 95% confidence interval:

- ✓ Main analysis will compare the incidence of each outcome for matched subjects with adjustment for drugs predisposing to bleeding during drug exposure (time dependant variables).
- ✓ Secondary analysis will compare the incidence of each outcome with all subjects, with adjustment for hdPS and drugs predisposing to bleeding during drug exposure (time dependant variable) for the rivaroxaban versus VKA comparison, and plus low or high DOAC dosage at index date for the rivaroxaban versus dabigatran comparison.
- ✓ Prognostic analysis will be done with all subjects to assess outcome risk factors, including gender, age, CHA2DS2-VASc and HAS-BLED scores, low or high dosage at index date for DOAC, drug predisposing to bleeding during drug exposure (time dependant variable) and significant baseline characteristics. The significant baseline characteristics will be identified firstly with univariate analyses, and therefore using a forward stepwise (taking into account the size of the database, the p threshold will be set at 1/1000 for variables selection and at 5% for the stepwise procedure).
- Estimation of cumulative incidence of each outcome during post-anticoagulant exposure period for rivaroxaban, dabigatran, and VKA (i.e. after anticoagulant discontinuation), using Kaplan-Meier estimate for death, cumulative incidence function for clinical outcomes (stroke and SE, ACS, CRB), in order to take into account death as a competing risk.
- Description of healthcare resources use and cost, for all and matched subjects according to the treatment group rivaroxaban dabigatran, and VKA during the first year of follow-up for all patients, and during two years of follow-up for those included in 2013. Comparison (rivaroxaban versus VKA, and rivaroxaban versus dabigatran) will be done for matched cohorts.

MILESTONES		

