9.5. STUDY SIZE

The Bordeaux Pharmacoépi (BPE) has performed a previous VKA study in the EGB database, a 1/97 permanent random sample of the SNIIRAM, using similar definitions used in this protocol (Blin 2015). Between 2007 and 2011, the numbers of subjects who initiated a VKA for SPAF were 2 197 for the specific NVAF population and 3 345 for the sensitive NVAF population, which represent about 50 000 and 75 000 subjects respectively in the SNIIRAM each year, and 100 000 and 150 000 respectively for a two-year inclusion period.

Among them, the number of subjects treated with rivaroxaban, dabigatran, and VKA, as well as the number of subjects who can be matched for each comparison (rivaroxaban versus VKA, rivaroxaban versus dabigatran) will be a result of the study. Anyway, it should be clearly higher than the 7 131 and 7 133 subjects randomized in the rivaroxaban and VKA arms of the ROCKET AF trial (Patel 2011).

In the previous VKA study cited above (Blin 2015), the outcome incidence rate during VKA exposure was estimated in the specific NVAF population (with similar results for the sensitive NVAF population):

- Stroke and systemic arterial embolism: 1.6 per 100 person-years (PY), 95%CI [1.1-2.1],
- ACS: 1.6 per 100 PY, 95%CI [1.0-2.1],
- CRB: 2.6 per 100 PY, 95%CI [1.9-3.3], with 0.5 [0.3-0.9] cerebral bleeding hospitalisation, 0.8 [0.4-1.1] digestive bleeding hospitalisation, and 1.3 [0.9-1.8] other bleeding hospitalisation,
- Death: 3.5 per 100 PY, 95%CI [2.7-4.3].

Within the ranges of incidence rates of ROCKET AF trial outcomes, the following table shows the minimum hazard ratio that can be identified with a 95% confidence interval excluding 1, for the study group compared to a reference group, according to the incidence of an outcome in the reference group and the sample size for each group for analysis of matched subjects (1:1).

Minimum hazard ratio (< 1 and > 1) with a 95% confidence interval excluding 1, for the study group compared to a reference group, according to the incidence of an outcome in the reference group, sample size for each group (1:1 matching) and normal distribution

Incidence in the reference group	Hazard ratio	Sample size			
		5 000	10 000	15 000	20 000
0.5%	< 1 / >1	0.24 / 2.19	0.43 / 1.78	0.58 / 1.52	0.65 / 1.42
1.0%	< 1 / >1	0.43 / 1.78	0.58 / 1.52	0.70 / 1.35	0.75 / 1.28
1.5%	< 1 / >1	0.53 / 1.61	0.66 / 1.41	0.75 / 1.28	0.79 / 1.23
2.0%	< 1 / >1	0.59 / 1.52	0.70 / 1.35	0.78 / 1.24	0.82 / 1.20

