9.7.1. Outcomes

Outcomes will be analysed using survival methods for the first occurrence of each outcome:

- Estimation of the one-year and two-year cumulative incidence of each outcome, and according to individual diagnose of each outcome, during drug exposure for rivaroxaban, dabigatran, and VKA, using Kaplan-Meier estimate for death and cumulative incidence function for clinical outcomes, in order to take into account death as a competing risk.
- Estimation of the incidence rate (per 100 PY exposed) of each outcome, and according to individual diagnose of each outcome, during drug exposure or if the risk is not constant over the time, during periods with a constant risk.
- Comparison of the one-year and two-year risk of each outcome during drug exposure, rivaroxaban versus VKA, and rivaroxaban versus dabigatran, using Cox proportional hazard risk model (Cox 1972) for death and Fine and Gray model (Fine 1999) for clinical outcomes, in order to take into account death as a competing risk. Hazard ratio will presented as a point estimate with its 95% confidence interval.
 - Main analysis will compare the incidence of each outcome for matched subjects with time dependant variables adjustment for drug predisposing to bleeding during drug exposure (time dependant variable),
 - Secondary analysis will compare the incidence of each outcome with all subjects, except outliers, with adjustment for hdPS and drug predisposing to bleeding during drug exposure (time dependant variable) for the rivaroxaban versus VKA comparison; and plus low or high DOAC dosage at index date for the rivaroxaban versus dabigatran comparison.
 - Prognostic analysis will be done with all subjects, but outliers, to assess outcome risk factors, including gender, age, CHA₂DS₂-VASc and HAS-BLED scores, low or high dosage at index date for DOAC, drug predisposing to bleeding during drug exposure (time dependant variable) and significant baseline characteristics. The significant baseline characteristics will be identified firstly with univariate analyses, and therefore using a forward stepwise (taking into account the size of the database, the p threshold will be set at 1/1000 for variables selection and at 5% for the stepwise procedure).

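### The risk-factor analysis screens additional baseline characteristics one at a time at p < 1/1000 and then steps forward, which can drop moderate, uncommon or masked factors and distort the estimates of those kept

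*Protocol*

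**What the plan says.** The rule is in the protocol itself, in the prognostic item of the Outcomes section (the second section numbered 9.7.1) and in the abstract under Data analysis. The abstract reads: "The significant baseline characteristics will be identified firstly with univariate analyses, and therefore using a forward stepwise". The body sets the limits: "the p threshold will be set at 1/1000 for variables selection and at 5% for the stepwise procedure". The reason offered is "taking into account the size of the database".

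Not everything is screened. Gender, age, CHA2DS2-VASc and HAS-BLED are named for inclusion, followed by "low or high dosage at index date for DOAC, drug predisposing to bleeding during drug exposure (time dependant variable) and significant baseline characteristics". Only that last group goes through selection.

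The item sits under a bullet that reports hazard ratios with 95% confidence intervals. The protocol mentions no shrinkage, bootstrap or other allowance for the selection.

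The analysis set differs between the two places. The body has "Prognostic analysis will be done with all subjects, but outliers", where section 9.7.3 defines outliers by lack of overlap of the hdPS distributions. The abstract has "Prognostic analysis will be done with all subjects to assess outcome risk factors", without that exclusion.

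**The concern.** Three features of the rule cause trouble.

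- The size of the database is a poor reason for a strict first threshold. In Cox and Fine-Gray models the information comes from events, and the rates in section 9.5 are low.
- A crude test asks the wrong question. A factor that matters after adjustment can look null on its own if it is correlated with another factor acting in the opposite direction. It is then removed before the multivariable step could find it.
- The factors that survive are reported as if they had been chosen in advance. Weak factors pass mainly when chance has inflated them, and leaving out correlated factors biases the rest.

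Assessing risk factors is a stated secondary objective. At stake are the published list of additional factors, the size of their hazard ratios and the meaning of their intervals.

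**Working it through.** The protocol gives no power or error rate for this analysis, so there is no stated figure to reproduce. The check has four steps.

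**1. Events.** Section 9.5 gives 2,197 specific-cohort VKA initiators over 2007 to 2011 in a 1/97 sample: 2,197 × 97 / 5 × 2 = about 85,240 subjects in two years. The protocol states about 100,000. Rates per 100 person-years are 1.6 (stroke/SE), 0.5 (cerebral bleeding) and 3.5 (death). Assuming one on-drug person-year each:

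- strokes: 85,240 × 0.016 = about 1,360, to 1,600;
- cerebral bleeds: about 430 to 500;
- deaths: about 2,980 to 3,500.

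The one-year assumption is not in the protocol. At 0.5 to 1.5 person-years, strokes would range from about 680 (85,240 × 0.5 × 0.016) to 2,400 (100,000 × 1.5 × 0.016).

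**2. The screen for one binary factor.** SE(log HR) = 1/√(events × p × (1 − p)), and p < 0.001 needs |z| > 3.29. With 1,360 events and prevalence 10% (assumed), SE = 1/√(1,360 × 0.09) = 0.0904.

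- Cut-off: exp(3.29 × 0.0904) = 1.35, or 1/1.35 = 0.74. At 680 and 2,400 events the upper cut-off is 1.52 and 1.25.
- True HR 1.20: z = 0.1823/0.0904 = 2.02. P(pass) = Φ(2.02 − 3.29) = 0.10; at 5% it would be Φ(2.02 − 1.96) = 0.52.
- Given that it passes, the mean log HR is 0.340, so the HR is about 1.41. Interval coverage is 0.0765/0.1015 = 75%.

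The same formula in other settings:

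| Events | Prevalence | True HR | Passes at 0.001 | Passes at 0.05 |
|---|---|---|---|---|
| 1,600 | 10% | 1.2 | 0.14 | 0.59 |
| 1,600 | 10% | 1.3 | 0.44 | 0.88 |
| 1,600 | 20% | 1.2 | 0.35 | 0.83 |
| 1,600 | 20% | 1.3 | 0.82 | 0.99 |
| 500 | 20% | 1.5 | 0.63 | 0.95 |

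At 20% prevalence, an 80% chance of passing needs HR 1.59, 1.29 and 1.19 at 500, 1,600 and 3,500 events.

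**3. Masking.** For standardised factors, crude log HR ≈ own log HR + r × the other's log HR. With an adjusted HR of 1.2 per SD, the other factor at 1.5 and r = −0.45: 0.182 − 0.45 × 0.405 = 0.000, a crude HR of 1.00. The factor passes with probability 0.001 at 500, 1,600 or 3,500 events, although its adjusted 5% test has power of at least 0.95. At r = −0.3 the crude HR is 1.063, and it passes with probability 0.19 at 1,600 events and 0.62 at 3,500.

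**4. The whole rule.** This was simulated on score statistics with 6 covariates forced in and 40 candidates, 12 of them real (HR 1.05 to 1.40 per SD). All of these are assumed settings. Correlated means mean |r| 0.11, maximum 0.45.

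| Events | Covariates | Real factors left out by the rule | Not significant at 5% in one full model | Coverage, selected factors | Coverage, forced-in factors |
|---|---|---|---|---|---|
| 500 | correlated | 68% | 40% | 0.89 | 0.91 |
| 1,600 | correlated | 53% | 16% | 0.76 | 0.89 |
| 3,500 | correlated | 43% | 5% | 0.62 | 0.84 |
| 500 | independent | 61% | 35% | 0.93 | 0.95 |
| 1,600 | independent | 31% | 11% | 0.94 | 0.95 |
| 3,500 | independent | 13% | 3% | 0.95 | 0.94 |

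Coverage in the full model was 0.95 in every row.

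**The case against.** The best defence is that a strict threshold in a large database keeps trivial associations out, and that the factors clinicians care about most are protected. Much of this stands. The named factors cannot be dropped, and through the two scores they carry heart failure, hypertension, diabetes, stroke, vascular disease, renal and liver dysfunction and bleeding history. Common, strong additional factors also pass.

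False positives are a real trade-off. With 28 null candidates, a full model flags 28 × 0.05 = 1.4 by chance. In the correlated simulation, nulls were 3%, 10% and 21% of selected factors at 500, 1,600 and 3,500 events. That is about 0.1, 0.6 and 1.8 nulls, for example 12 × 0.574 × 0.207/0.793 = 1.8. So the rule protects at low event counts but not at high ones, where nulls stand in for omitted correlated factors.

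Four stronger readings are tempting, and the documents do not support them.

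- *The intervals are simply too narrow.* Part of the loss is bias from selection and omission, and it nearly vanishes with independent covariates.
- *Every outcome has more than 1,000 events, so selection is never needed.* Section 9.5 gives no rate for major bleeding, and cerebral bleeding yields only about 430 to 500 events.
- *The outlier exclusion is undefined because the model pools three drugs.* The protocol does not say that it pools them. The item sits under the two pairwise comparisons, and read that way each hdPS defines its own outliers. The abstract also omits the exclusion from the secondary analysis, so it may just be abbreviated.
- *Section 9.7.5 already supplies a candidate list.* It names no individual variables, and the ENCePP checklist leaves comorbidity detail to the SAP.

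**Conclusion.** The point holds for the additional baseline characteristics only. Among these, moderate or uncommon factors, and factors masked in crude analysis, will often be left out. Weak factors that pass have inflated hazard ratios. Nominal 95% intervals can fall below 95% coverage when covariates are correlated, which is plausible for comorbidities linked through age and frailty. The intervals of the named factors can suffer too.

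The sizes rest on assumed prevalences, correlations, candidate numbers and one on-drug person-year per subject, so they show what the rule can do and do not forecast this study's results. Exclusion of a fully masked factor does not depend on sample size.

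This is worth changing because the protocol fixes the rule for a stated secondary objective. The matched and hdPS-adjusted drug comparisons do not use the selection and are not affected.

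**What to change.** In the Outcomes section and the abstract:

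- Delete the univariate screen and the forward stepwise step.
- State that candidate baseline characteristics are listed before analysis (the list itself can sit in the SAP), that one multivariable model is fitted per outcome, and that every hazard ratio is reported with its 95% interval.
- Enter either the risk scores or their components, not both, because the scores are sums of the components and would be collinear with them.
- For outcomes with few events, use a penalised fit, or backward elimination from the full model with the whole selection bootstrapped, and label the result exploratory.
- Give the same analysis set in both places, without trimming on hdPS overlap. That trimming serves the drug comparison and has no role in a risk-factor model.

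The cost is a change of wording, a longer results table and slightly wider intervals. No new data are needed.

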9.7.2. Healthcare resources and cost

Healthcare resources and cost will be described for all and matched subjects according to the treatment group (rivaroxaban, dabigatran, VKA) during the first year of follow-up for all patients, and during two years of follow-up for those included in 2013. Comparison (rivaroxaban versus VKA, and rivaroxaban versus dabigatran) will be done for matched cohorts.

9.8. QUALITY CONTROL

The Bordeaux Pharmacoépi, INSERM CIC1401, has implemented a quality management system for all its activities. CNAMTS data extraction will be validated

using the expected population size estimated using the EGB. An independent double programming will be performed for main criteria and analyses, and the results compared for validation. All statistical logs are kept and can be provided. In the case of interim analyses, the database for the interim analysis is locked and kept for ulterior validation if needed. The statistical analysis report (SAR) is included in the final study report.

9.9. LIMITATIONS OF THE RESEARCH METHODS

The SNIIRAM is a national healthcare claims database linked to the national hospital discharge summaries database that covers more than 95% of the French population. It provides a unique opportunity to identify all new users of DOAC or VKA in NVAF in 2013-2014, with exhaustive information about reimbursed treatments out of hospital and use of reimbursed healthcare resources, as well as all hospitalisations for the outcomes of interest. Furthermore, the SNIIRAM has the advantage of any study extracting patient records from an existing database that are not impacted by the study.

This is also the main limit of this claims and hospitalisation database that was built for administrative and reimbursement purposes with a lack of clinical data and biological results, including some risk factors such as smoking status, body mass index, blood pressure, and cholesterol values, that could be impact the patient prognosis. However, statistical methods such as PS and hdPS were developed to improve control of confounding using a large number of covariates ascertained from patients' healthcare claims data, as these variables may collectively be proxies for unmeasured confounders (Schneeweiss 2009, Rassen 2012).

Selection bias

Since all subjects identified with extraction criteria in 2013-2014 will be extracted from a national database, there is no study selection bias, nor attrition bias, except very rare withdrawals from one of the healthcare insurance systems including and covering more than 95% of the French population.

Information bias

- **AF indication:** Anticoagulants are prescribed for several medical conditions. The main analysis will be done using the specific NVAF population, with a highly specific definition of the disease (LTD for AF or a hospitalisation with an AF diagnosis before the index date). Nevertheless, several subjects with an AF do not have an LTD and are not hospitalized or hospitalized for another primary diagnosis without AF reported in the linked or associated diagnosis, during the 3 years before index date. To assess the robustness of the main analysis results, secondary analyses will be performed using a sensitive definition for NVAF (sensitive NVAF population) defined as the subjects of the specific NVAF population, plus those with probable information using an AF disease score. In terms of bias, there is no reason that the specificity of AF definition will be different according to the treatment group.
- **Drug exposure:** VKA and DOAC exposure will be assessed using exhaustive non-hospital drug claims. Drugs prescribed during hospital stays are not recorded and could represent a potential risk of exposure underestimation. However, it should concern few subjects for a very short period of time, and the impact over a 3-year study period should be negligible. Drug expose is defined as the time between index date and the end of follow-up for subjects without drug withdrawal, i.e. as the time between index date and last dispensation + 90 days (30 days for the duration of the

last dispensation or less for small DOAC packaging, plus a grace period of 60 days), or before in case of drug switch. Two grace periods will be considered (60 and 30 days) to estimate the true drug withdrawal, in order to take into account the drug supply in real life, or short discontinuation and bad drug adherence that could be a risky situation for ischemic event, directly in relation with the use of the DOAC or VKA. This would also cover short hospital stays.

- **Outcomes:** Since deaths are recorded in the database using the national death registry, there is no information bias for this outcome. Death is a competing risk of other clinical outcomes (stroke and SE, ACS, CRB). To take into account this, the model proposed by Fine and Gray will be used to analyse clinical outcomes (Fine 1999). Clinical outcomes will be defined using the ICD-10 discharge primary diagnosis. Miscoding cannot be excluded but should be sparse for the clearly defined events studied. Nevertheless, the PMSI coding is fully independent from the study and there is no reason that a potential miscoding will be different between anticoagulant drugs, excluding an information bias. For strokes classified as undefined because CT scan or NMR were not performed, it was decided to classify undefined stroke with ischemic stroke but some could be cases of haemorrhagic stroke. A sensitivity analysis will be performed by classifying undefined stroke as haemorrhagic stroke.

Counfounding bias

The choice between a VKA and a DOAC could be related to potential confounding. To control this potential bias, the main analysis will use 1:1 matching on high dimensional propensity score (hdPS), which includes main known risk factors (gender, age, AF risk factor score, bleeding risk factor score). Indeed, one of the main limits of this database, as for many administrative databases, is the lack of information for some risk factors (e.g. smoking status, body mass index, biological results, etc.), which may or not be confounders. Without such information, it is not possible to compare the distribution of these risks factors between treatment groups, or to take it into account in the matching.

The propensity score is a statistical technique that attempts to estimate the effect of a treatment, policy, or other intervention by accounting for the covariates that predict receiving the treatment. The propensity score, and more recently hdPS (Schneeweiss 2009, Rassen 2012), were developed to summarise a large set of variables that characterize each subject for status and unmeasured confounders not recorded in a database (i.e. drugs, medical status, hospitalisation, other co-morbidities directly, or indirectly linked with unmeasured confounders). Adjusting for large numbers of covariates ascertained from subject healthcare claims data may improve control of confounding, as these variables may collectively be proxies for unobserved factors.

9.10. OTHER ASPECTS

None.

10. PROTECTION OF HUMAN SUBJECTS

This project is a database analysis with individual anonymous information for which subject informed consent is not required. Data extraction from the SNIIRAM is regulated and needs approval from Institute of Health Data (*Institut des Données de Santé - IDS*)

and French data protection commission (*Commission Nationale de l'Informatique et des Libertés* - CNIL).

11. MANAGEMENT AND REPORTING OF ADVERSE EVENTS/ADVERSE REACTIONS

This project is a database analysis using anonymous individual information without any spontaneous reporting. Study outcomes will be reported in aggregate in the final study report, and no individual or expedited reporting is required, according to the EMA Guideline on good pharmacovigilance practices cited above (GVP IV*), as well as the ENCePP Guide on Methodological Standards in Pharmacoepidemiology.

* The latest revision of the Guideline on good pharmacovigilance practices (GVP) Module VI – Management and reporting of adverse reactions to medicinal products (Rev 1) from EMA (coming into effect 16 Sept 2014) specifies: *For Non-interventional post-authorisation studies based on secondary use of data (VI.C.1.2.1.b): “The design of such studies is characterised by the secondary use of data previously collected from consumers or healthcare professionals for other purposes. Examples include medical chart reviews (including following-up on data with healthcare professionals), analysis of electronic healthcare records, systematic reviews, meta-analyses. For these studies, the reporting of suspected adverse reactions in the form of ICSRs is not required. Reports of adverse events/reactions should be summarised as part of any interim safety analysis and in the final study report unless the protocol provides for different reporting”.*

